17 EFFICACY

17.1 Primary and Secondary Efficacy Variables

In order to satisfy different health authority requirements, the primary variables will be tested with 2 response endpoints:

- Successful Early Clinical Response (72-120 hours after first dose) will be determined programmatically and defined as survival with improvement in at least 2 of 4 subject symptoms (cough, sputum production, pleuritic chest pain, dyspnea), as assessed by the investigator, without deterioration in any of these 4 symptoms.
- Successful Investigator's Assessment of Clinical Response at the PTE visit, defined as survival after completion of a test article regimen, with resolution of signs and symptoms of the infection to the extent that further antibacterial therapy is not necessary.

The Early Clinical Response endpoint will be the primary efficacy outcome supporting registration with the FDA in the US and this will be tested in the intent-to-treat (ITT) analysis population. The Investigator's Assessment of Clinical Response at PTE endpoint will be the primary efficacy outcome supporting registration with the EMA in the European Union (EU) and will be tested in the ITT and clinically evaluable (CE) populations (co-primary endpoints). The analysis of the Investigator's Assessment of Clinical Response at PTE as the primary efficacy outcome will be detailed in a separate SAP for the EMA.

Secondary efficacy variables will include:

- Response category for Early Clinical Response
- Clinical Response category for Investigator's Assessment of Clinical Response at EOT and PTE
- Clinical Response category according to the identified causative pathogen

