17.2.3.3 Clinical Evaluation of the Infection Under Study at PTE

The PTE assessment is to be performed 5 to 10 days after the subject's last day of therapy. The investigator will determine whether or not the subject meets the criteria of 1 of the following clinical outcomes:

Clinical Success: survival after completion of a test article regimen without receiving any systemic antibacterial therapy other than test article, resolution of signs and symptoms of the infection present at Screening with no new symptoms or complications attributable to CABP and no need for further antibacterial therapy.

Clinical Failure: the subject requires alternative antibacterial treatment for CABP prior to PTE related to either (a) progression or development of new symptoms of CABP or (b) development of infectious complications of CABP (eg, empyema, lung abscess).

- The subject is receiving antibiotics that may be effective for the infection under study for a different infection from the 1 under study.
- Death prior to PTE.

Indeterminate: the clinical response to test article could not be adequately inferred due to:

- Subjects were not seen for PTE evaluation because they withdrew consent, were lost to follow-up, other (specify).
- Other specified reason.

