5.2.2 Secondary Efficacy Outcomes

5.2.2.1 Investigators Assessment of Clinical Response

The investigator will make an assessment of Clinical Response at the EOT and PTE Visits, based on the definitions below. The secondary efficacy outcome is the overall assessment of clinical response at PTE (derived from the investigator assessments at the EOT and PTE Visits) in the ITT and CE-PTE populations as defined in [Table 3](#).

EOT Visit

At the EOT Visit (on the calendar day of, or within 2 days following the last dose of test article), the investigator will indicate the clinical status of the infection under study as detailed below.

Clinical Success: the subject is alive and the infection is sufficiently resolved such that further antibacterial therapy is not needed. These subjects may have some residual findings related to infection (ie, cough) requiring ancillary (ie, non-antibiotic) treatment (eg, expectorant). In order for the subject to be considered a Clinical Success at EOT, the subject may not meet any criteria for Clinical Failure or Indeterminate at EOT.

Clinical Failure: the subject requires alternative antibacterial treatment for CABP prior to EOT related to either (a) progression or development of new symptoms to CABP or (b) development of infectious complications of CABP (eg, empyema, lung abscess) or (c) subject developed an AE that required discontinuation of study therapy prior to the EOT. Other reasons for clinical failure are:

- Subject is receiving antibacterial therapy that may be effective for the infection under study for a different infection from the one under study.
- Death prior to EOT.

Indeterminate: the clinical response to test article could not be adequately inferred due to:

- Subjects were not seen for EOT evaluation because they withdrew consent, were lost to follow-up, other reason (specify).
- Other specified reason.

PTE Visit

At the PTE Visit (5 to 10 days after the subject's last day of study therapy) the investigator will indicate one of the following outcomes relating to the primary infection under study:

Clinical Success: survival after completion of a test article regimen without receiving any systemic antibacterial therapy other than test article, resolution of signs and symptoms of the infection present at Screening with no new symptoms or complications attributable to CABP and no need for further antibacterial therapy.

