Clinical Failure: the subject requires alternative antibacterial treatment for CABP prior to PTE related to either (a) progression or development of new symptoms of CABP or (b) development of infectious complications of CABP (eg, empyema, lung abscess). Other reasons for clinical failure are:

- The subject is receiving antibiotics that may be effective for the infection under study for a different infection from the one under study.
- Death prior to PTE.

Indeterminate: the clinical response to test article could not be adequately inferred due to:

- Subjects were not seen for PTE evaluation because they withdrew consent, were lost to follow-up, other (specify).
- Other specified reason.

Overall Clinical Response at PTE (based on the investigator's assessment) is determined as follows from the investigator's assessments at the EOT and PTE Visits:

Table 3. Investigator's Assessment of Clinical Response

EOT Visit	PTE Visit	Overall Assessment of Clinical Response at PTE Visit
Success	Success	Success
Success	Failure	Failure
Success	Indeterminate	Indeterminate
Failure	Success	Failure
Failure	Failure	Failure
Failure	Indeterminate	Failure
Indeterminate	Success	Indeterminate
Indeterminate	Failure	Failure
Indeterminate	Indeterminate	Indeterminate

Abbreviations: EOT = end of treatment; PTE = post-therapy evaluation.

For the ITT population, the proportion of ITT subjects with a Clinical Success is defined using the following formula (where the denominator adds to the total number of subjects in the ITT population):

Number of subjects with Clinical Success

(Number of subjects with Clinical Success + Number of subjects with a Clinical Failure + Number of subjects with an Indeterminate response)

By definition, subjects in the CE-EOT and CE-PTE populations cannot have an Indeterminate response. Thus, for the CE-EOT and CE-PTE populations, the proportion of subjects with a Clinical Success is defined using the following formula:

Number of subjects with Clinical Success

(Number of subjects with Clinical Success + Number of subjects with a Clinical Failure)

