6.1.4.3 Concomitant Antibiotic Therapy

Subjects who receive any systemic concomitant antibiotic therapy from the time of the first dose of test article through the time of the last dose of test article at EOT and through the PTE Visit with a spectrum of activity against the known or potential infecting pathogen(s) responsible for the CABP under study will be excluded from the CE-EOT and CE-PTE populations, respectively, unless the subject receives the antibiotic therapy for treatment of the CABP due to insufficient therapeutic effect of the test article (ie, for progression or development of new symptoms of CABP or development of infectious complications of CABP).

Subjects who receive a systemic concomitant antibiotic that is not effective against the baseline pathogen, or if no pathogen is isolated, and the antibiotic does not have activity against CABP pathogens, will be included in the CE-EOT and CE-PTE populations.

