6.1.4.5 Clinical Outcome Assessment

Subjects must meet the following to be included in the CE populations:

- For the CE-EOT population:
 - Completed the investigator's assessment of clinical response (ie, was not deemed an indeterminate outcome) at the EOT Visit, and
 - The EOT Visit occurred on the day of, or within 2 days following the last dose of test article.
- For the CE-PTE population:
 - The overall Clinical Response (based on the investigator's assessment) at the PTE Visit is not Indeterminate.
 - The PTE Visit occurred 5 to 10 days after the last dose of test article, unless the subject was considered to be a Clinical Failure based on the investigator's assessment at the EOT Visit or the patient died after EOT and before PTE.

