 - If the time of administration of the first dose of test article is missing, the subject will be defined as an Indeterminate response (unless the subject is considered a Clinical Failure for another reason) which is essentially a Clinical Failure for the primary analysis in the ITT population.
- For the secondary outcome measures (investigator's assessment of Clinical Response at the EOT and PTE Visits):
 - Subjects will be defined as an Indeterminate if the investigator cannot determine whether the subject is a Clinical Success or Failure at the EOT or PTE Visits or the subject has a missing response (see [Table 1](#)). By definition, subjects with an Indeterminate response are included in the denominator for analyses in the ITT and

microITT populations, and thus, are considered Clinical Failures. Subjects with an Indeterminate response are excluded from the CE-EOT, CE-PTE, ME-EOT and ME-PTE populations.

- For microbiologic response:
 - If no post-baseline source specimen is obtained and the subject has an investigator’s assessment of Clinical Response, the per-pathogen microbiological response is based on the investigator’s assessment of Clinical Response (ie, the response is a presumed response). A per-pathogen microbiological response at the EOT Visit or PTE Visit will be considered Indeterminate only if the Clinical Response at EOT or PTE is also Indeterminate.
- Missing values for other individual data points will remain as missing. Missing values will not be imputed and only observed values will be used in data analyses and presentations.
- Where individual data points are missing, categorical data will be summarized based on reduced denominators (ie, only subjects with available data will be included in the denominators).

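### PTE Clinical Success bars every other systemic antibacterial, while the neighbouring definitions bar only agents that may act on the pneumonia, so a resolved subject given an inactive agent has no clear category

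*Combined protocol and SAP*

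**What the plan says.** Protocol v2.0, 17.2.3.3, makes PTE Clinical Success conditional on "survival after completion of a test article regimen without receiving any systemic antibacterial therapy other than test article", together with resolution of the presenting signs and symptoms and no further need for treatment. SAP 5.2.2.1 repeats the clause: "without receiving any systemic antibacterial therapy other than test article". Neither text limits it by spectrum or by reason for use.

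The surrounding rules are narrower or silent:

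- **PTE Failure, SAP 5.2.2.1.** Treatment of a second infection counts as failure only in this case: "The subject is receiving antibiotics that may be effective for the infection under study for a different infection from the one under study".
- **EOT Success, SAP 5.2.2.1.** It has no bar on other antibacterials. It adds that "the subject may not meet any criteria for Clinical Failure or Indeterminate at EOT", and the EOT Failure bullet has the same limit to potentially effective agents.
- **Summary definition of PTE success, Protocol 17.1.** Survival after the regimen "with resolution of signs and symptoms of the infection to the extent that further antibacterial therapy is not necessary", with no bar on other agents.
- **CE rule on concomitant antibiotics, SAP 6.1.4.3.** Exclusion depends on activity. Subjects whose agent was not effective against the baseline pathogen, or, where none was isolated, "and the antibiotic does not have activity against CABP pathogens, will be included in the CE-EOT and CE-PTE populations".
- **CE-PTE outcome requirement, SAP 6.1.4.5.** The overall response "at the PTE Visit is not Indeterminate". SAP 8.3 agrees: "Subjects with an Indeterminate response are excluded from the CE-EOT, CE-PTE, ME-EOT and ME-PTE populations".

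**The concern.** Take a subject who was a Success at EOT, whose pneumonia has resolved by PTE, and who received a systemic antibacterial with no relevant activity for an unrelated infection. The Success clause shuts this subject out, and the Failure bullets do not take the subject in. The investigator has three boxes, and the only one left is Indeterminate.

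In ITT that counts against the treatment. In CE-PTE the subject disappears, although 6.1.4.3 says that this kind of agent is no reason for exclusion. Because the investigator assigns the outcome, at up to about 150 sites (Protocol 11.6), one site may follow the Success clause and another may judge that the response is plainly a success. The same clinical course can then be analysed in two ways.

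What is at stake is the PTE endpoint. SAP 10.3 treats its intervals as descriptive. Protocol 22.4.3 makes the same outcome, in ITT and CE, the EMA primary analysis. The EMA SAP is not among the documents, so the protocol wording has to be taken as applying unless that SAP changes it.

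**Working it through.** **Tracing the subject through the rules**

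1. PTE Success: not met, because another systemic antibacterial was received.
2. PTE Failure: not met. There was no alternative treatment for the pneumonia, no potentially effective agent for another infection, and no death.
3. PTE Indeterminate: reached only by elimination, through its open-ended other-reason entry.
4. SAP Table 3: EOT Success with PTE Indeterminate gives overall Indeterminate. (Had EOT been Failure, the overall result would be Failure whatever the clause says.)
5. ITT: the subject stays in the denominator and is a non-success. CE-PTE: excluded under 6.1.4.5 and 8.3.

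**Inputs for size.** SAP 5.1.1: margin 0.10, 1-sided alpha 0.0125 (z = 2.2414), ITT rate 79% with 638 subjects, CE rate 85% with 510 subjects. Allocation is 1:1, so 319 and 255 per arm. The share affected, f, is not in the documents. I assume 0.5%, 1% and 2%, equal in both arms, with every such subject coded Indeterminate.

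**Formula (Farrington–Manning, equal true rates p).** Power = Φ[(0.10 − z·s0)/s1], where s1 = √[2p(1−p)/n] and s0 = √{[a(1−a) + b(1−b)]/n}. Here a and b are the maximum-likelihood rates constrained to a − b = −0.10.

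**Reproducing the plan**

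- ITT, p = 0.79, n = 319: a = 0.7316, b = 0.8316, s0 = 0.03247, s1 = 0.03225. (0.10 − 2.2414 × 0.03247)/0.03225 = 0.844, so power = 0.8006 (plan: 80%). Solving for n gives 318.5, hence 2 × 319 = 638.
- CE, p = 0.85, n = 255: a = 0.7874, b = 0.8874, s0 = 0.03238, s1 = 0.03162. The ratio is 0.867, so power = 0.8071 (plan: 81%).

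**With the clause applied literally.** In ITT the rate becomes 0.79 − f. In CE-PTE, f is taken as a share of CE subjects, so n = 255(1−f) and p = (0.85−f)/(1−f).

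| f | ITT rate | ITT power | CE n per arm | CE rate | CE power |
|---|---|---|---|---|---|
| 0 | 79.0% | 80.1% | 255 | 85.0% | 80.7% |
| 0.5% | 78.5% | 79.4% | 253.7 | 84.9% | 80.3% |
| 1% | 78.0% | 78.7% | 252.5 | 84.8% | 80.0% |
| 2% | 77.0% | 77.4% | 249.9 | 84.7% | 79.2% |

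**Effect on the interval.** Unstratified Miettinen–Nurminen 97.5% lower bounds, with the same counts in both arms:

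- ITT, n = 319: 252 successes give −7.26%. Recoding 3 per arm (249; 3/319 = 0.9%) gives −7.37%, and 6 per arm (246; 6/319 = 1.9%) gives −7.48%.
- CE-PTE: 217/255 gives −7.17%. Removing 5 resolved subjects per arm (5/255 = 2.0%) leaves 212/250 and gives −7.30%.

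The EMA interval is stratified, so these bounds are indicative only.

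**The case against.** The strongest reply is that nothing in the plan actually sends this subject to Indeterminate. That category is meant for responses that could not adequately be inferred, and SAP 8.3 uses it when the investigator cannot decide or the response is missing. A resolved pneumonia with an irrelevant antibiotic fits neither description well. SAP 5.2.2.1 asks for an outcome of the infection under study, Protocol 17.1 has no bar, and 6.1.4.3 means to keep such subjects. Read as a whole, the plan leans towards Success. This stands as far as it goes: Indeterminate follows by elimination, not by rule. But the Success clause is equally explicit the other way and no text settles the matter, so inconsistent coding remains possible.

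The affected group is also narrow, the assumed frequencies have no support in the documents, and coding every case as Indeterminate is the extreme. The plan does not say whether its 79% already allows for such cases. All of this stands.

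A reader might infer more, in three directions the documents do not support:

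- **That the clause flatly contradicts 6.1.4.3 or empties it.** The CE criteria apply jointly, so inclusion there can mean not excluded on that criterion. The rule still excludes subjects given active agents, and its inclusion sentence works in full for CE-EOT.
- **That PTE Success is defective for lacking the sentence in EOT Success that rules out anyone meeting a Failure or Indeterminate criterion.** PTE Success as written already excludes every PTE Failure criterion, and that sentence would not help a subject who meets none of them.
- **That one arm would suffer more.** If only omadacycline subjects were affected, ITT power would be 75.1% at 0.5% and 69.7% at 1%, but nothing in the documents gives reason to expect it.

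**Conclusion.** The mismatch is real and the point is minor. One clause is broader than the definitions around it. It leaves a resolved subject given only an inactive agent outside both PTE Success and PTE Failure, with the coding left to each site.

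Under the balanced, all-Indeterminate assumption, a share of 0.5% to 2% costs 0.7 to 2.7 points of ITT power (80.1 − 79.4; 80.1 − 77.4) and 0.4 to 1.5 points of CE power (80.7 − 80.3; 80.7 − 79.2). It moves the lower bounds in the examples by about 0.1 to 0.2 points, against a margin of −10%. The true share is unknown, and mixed coding would give a smaller effect.

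It would be wrong to infer a threat to the FDA primary conclusion: Early Clinical Response does not use this definition. In this SAP PTE supports no non-inferiority claim. The relevance is to the EMA primary analysis, whose own SAP cannot be checked here.

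**What to change.** Before unblinding:

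1. In Protocol 17.2.3.3 and SAP 5.2.2.1, and in the EMA SAP if it repeats the clause, limit the bar in PTE Success to non-study systemic antibacterials that may be effective for the infection under study, using the qualifier already in the PTE Failure bullet.
2. Have the blinded Evaluability Review Team (SAP 6.2) identify every subject whose only non-study systemic antibacterial was inactive against the pneumonia, and query the PTE outcome whether it was recorded as Success or Indeterminate. Querying Indeterminates alone could only move subjects towards Success. The query is needed because new wording does not alter outcomes already recorded.
3. Report one ITT sensitivity analysis of PTE response under the present literal wording, with receipt of any other systemic antibacterial counted as not a Success.

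The cost is a short written protocol amendment (Protocol 29.1) to a definition that is secondary here and primary for the EMA, one query step and one extra table. No new data are needed, since Protocol 13 already has all medications after the start of test article recorded in the eCRF.

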5.2.2.2 Microbiologic Outcomes

Microbiological response definitions for the evaluations performed at the EOT and PTE Visits and analyzed in the microITT and ME populations are presented in the table below. Post-baseline microbiological samples will be collected only as clinically indicated. Atypical pathogens identified only by acute and convalescent serology or baseline urinary antigen tests (UAT), and *Streptococcus pneumoniae* identified only by baseline UAT can only have a presumed or indeterminate microbiologic response.

If a subject has the same pathogen (ie, same genus and species) identified from both a respiratory and blood specimen, a microbiological response is determined for each of the pathogens. The microbiologic response for the respiratory pathogen is based on the pathogen isolated from the EOT or PTE specimen, if a specimen was collected. The microbiologic response for the blood pathogen is based on the blood sample collected at EOT or PTE, or if a sample was not collected at the post-baseline visit, the blood sample collected prior to and closest to the visit. For the pathogen specific microbiologic response, the worst outcome for the pathogen should be summarized. If *Streptococcus pneumoniae* is identified from both a UAT and a culture, the culture should be used to determine microbiological response.

Table 4. Per-Pathogen Microbiological Response Definitions at the EOT and PTE Visits

Term	Definition
Eradication	The baseline pathogen based on culture was absent from repeat culture(s) of the same sample type (blood or respiratory specimen).
Presumed Eradication	No post-baseline source specimen to culture in a subject assessed with a clinical success by the Investigator
Persistence	The baseline pathogen based on culture was present in repeat culture(s) of the same sample type (blood or respiratory specimen).
Presumed Persistence	No post-baseline source specimen to culture in a subject assessed with a clinical failure by the Investigator
Indeterminate	The subject's clinical response is indeterminate or other circumstance that precludes a microbiological evaluation

Abbreviations: EOT = end of treatment; PTE = post-therapy evaluation.

Microbiological outcomes are further categorized as favorable, unfavorable, and indeterminate. Favorable microbiological outcomes are defined as eradication or presumed eradication. Unfavorable microbiological outcomes are defined as persistence or presumed persistence. Microbiological response will be derived using electronic microbiology data from the central laboratory and from pathogen determination provided by the Sponsor for each baseline isolate.

Overall microbiological response at PTE is determined as follows from the microbiological responses at the EOT and PTE Visits:

Table 5. Per-Pathogen Microbiologic Response

EOT Visit	PTE Visit	Overall Microbiologic Response at PTE
Favorable	Favorable	Favorable
Favorable	Unfavorable	Unfavorable
Favorable	Indeterminate	Indeterminate
Unfavorable	Favorable	Unfavorable
Unfavorable	Unfavorable	Unfavorable
Unfavorable	Indeterminate	Unfavorable
Indeterminate	Favorable	Indeterminate
Indeterminate	Unfavorable	Unfavorable
Indeterminate	Indeterminate	Indeterminate

Abbreviations: EOT = end of treatment; PTE = post-therapy evaluation.

Note: Favorable is defined as eradication or presumed eradication. Unfavorable is defined as persistence or presumed persistence.

Per-subject responses will be based on per-pathogen responses. To have an overall per-subject favorable microbiologic response, the outcome for each baseline pathogen must be favorable (eradicated or presumed eradicated). If the outcome for any pathogen is unfavorable (persistence or presumed persistence), the subject will be considered to have an unfavorable per-subject microbiologic response. Subjects with an indeterminate response for all pathogens will be considered to have an indeterminate per-subject microbiologic response. If the same pathogen is isolated from multiple sample types (blood, respiratory, urine), the worst outcome will be used to determine per-subject microbiologic response. Superinfections will not be considered in the microbiological response. Microbiological response from worst to best are as follows: persistence, presumed persistence, indeterminate, presumed eradication, and eradication.

The overall per-subject microbiologic response at PTE is determined from the per-subject microbiologic responses at the EOT and PTE Visits in the same manner as the per-pathogen microbiologic response in [Table 5](#). For subjects with a per-subject favorable response at the EOT Visit, the overall microbiologic response at PTE of eradication, presumed eradication, persistence, and presumed persistence are based on the response at the PTE Visit. For subjects with a per-subject unfavorable response at the EOT Visit, the overall microbiologic response at PTE of persistence and presumed persistence are based on the response at the EOT Visit except for when the response at the PTE Visit is unfavorable. In this case, the overall microbiologic response at PTE of persistence and presumed persistence are based on the response at the PTE Visit. For subjects with a per-subject indeterminate response at the EOT Visit and unfavorable at the PTE Visit, the overall microbiologic response at PTE of persistence and presumed persistence are based on the response at the PTE Visit.

For the microITT population, the proportion of subjects with a favorable microbiological response is defined using the following formula (where the denominator adds to the total number of subjects in the microITT population):

$$\frac{\text{Number of subjects with eradication} + \text{Number of subjects with presumed eradication}}{(\text{Number of subjects with eradication} + \text{Number of subjects with presumed eradication} + \text{Number of subjects with persistence} + \text{Number of subjects with presumed persistence} + \text{Number of subjects with indeterminate response})}$$

By definition, the ME populations (ME-EOT and ME-PTE) must have sufficient information to determine the outcome and thus, excludes subjects with indeterminate responses. For the ME populations, the proportion of subjects with a microbiological response is defined using the following formula:

$$\frac{\text{Number of subjects with eradication} + \text{Number of subjects with presumed eradication}}{(\text{Number of subjects with eradication} + \text{Number of subjects with presumed eradication} + \text{Number of subjects with persistence} + \text{Number of subjects with presumed persistence})}$$

Microbiological response definitions of superinfection and new infection are presented in [Table 6](#) below:

Table 6. Microbiological Response Definitions: Superinfection or New Infection

Term	Definition
Superinfection	Isolation of a non-baseline pathogen from blood or respiratory cultures while the subject is on test article and the subject shows progression or development of new symptoms of CABP or development of infectious complications of CABP (ie, the subject is deemed a clinical failure by the investigator at the EOT Visit)
New infection	Isolation of a non-baseline pathogen from a post-treatment culture of a blood or respiratory specimen and the subject shows progression or development of new symptoms of CABP or development of infectious complications of CABP (ie, the subject is deemed a clinical failure by the investigator at the PTE Visit)

Abbreviations: CABP = community-acquired bacterial pneumonia.

For subjects with multiple microbiological samples taken either while the subject is on test article (for determination of superinfection) or post-treatment (for determination of new infection) all cultures will be used in the analysis.

